6.2.1.3 Health related QoL measure

Quality-of-life will be assessed using the Health Related Quality-of-Life Measure developed by the Centre for Disease Control and Prevention (CDC). There are four questions in this tool that measure self-perceived health, recent physical and mental health, and recent activity limitation (Ôunpuu et al., 2000). Although the SF-36 will be used in the gHQ, it's application in the health questionnaire and medical testing study is considered onerous given the amount of additional information being collected.

6.2.1.4 Current medical health status

The current medical health status section covers symptomatology, the presence and duration of disease, and information on drug use. Types of diseases assessed fall under categories such as respiratory, upper airway, skin, cardiovascular, thyroid, gastro-

intestinal/liver, neurological, and reproductive health. A question will also be asked about multiple chemical sensitivities.

6.2.1.5 Mental health

Mental Health will be assessed using the Bradburn Affect Balance Scale, a measurement tool that has been used by Statistics Canada in the Canadian Community Health Survey. There are eleven questions in this assessment tool for which their categorical responses will be summarized independently.

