SUBJECT PARTICIPATION	The health questionnaire consists of 104 questions that should take each individual approximately 30 minutes to complete. Medical testing will require blood and urine collection, skin sensitivity testing, pulmonary function testing, blood pressure and ECG. All testing will be acute except for skin sensitivity testing, where a patch will be applied to the skin and remain for a period of 48 hours. Informed consent must be obtained from the individual prior to answering the health questionnaire and undergoing medical testing. The informed consent advises individuals of the voluntary nature of participation, confidentiality of their results, study procedures, and the benefits and risks of study participation. For subjects between the ages of 12 – 17 parental/guardian consent is required in addition to the assent of the child/adolescent.
OUTCOME MEASURES	Outcome measures from this study will include:

	
 1. Current reported medical health status as determined by the health questionnaire; 2. Current reported psychosocial health status as determined by the Bradburn Affect Balance Scale and the Health Related Quality of Life-4 scale; 3. Additional reported demographic and exposure-related information based on residential address and occupational history; and 4. Current measured physical health status as determined by the medical test battery, including: haematology, urinalysis, blood biochemistry, cardiovascular and lung function, skin sensitivity, and Chemicals of Concern levels in the body.

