3.2.1.3.1 Mental health

Given the concern of residents over mental health issues, and the dynamic of the situation in Port Colborne, due attention is being given to the mental health of the community.

Eleven questions taken from the Bradburn Affect Balance Scale, a measurement of psychological well-being developed by Norman M. Bradburn, are included to establish the way the subject has felt over the past few weeks (Bradburn, 1969). Five questions reflecting positive feelings and five questions reflecting negative feelings as well as a

final question reflecting overall happiness comprise the Mental Health section of the questionnaire.

The CCHS also draws upon the Affect Balance Scale for questions relating to mood. Therefore, an extensive dataset exists for comparative analysis.

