3.2.1.3.2 Quality of life

In assessing general health, researchers and medical health experts have begun to pose health-related questions more broadly in terms of quality of life (QoL). In basic terms, QoL relates to general well-being, including happiness and satisfaction with life.

To measure QoL, the Health Related Quality of Life-4 (HRQoL-4) Questionnaire has been included in the health questionnaire. This four-item scale, a set of questions called Healthy Days measures, has been in continuous use in the U.S. state-based Behavioural Risk Factor Surveillance System, a division of the Center for Disease Control (CDC), since 1993. Unhealthy days are defined as the overall number of days during the previous 30 days when the respondent felt that either his/her physical or mental health was “not good,” and is calculated by summing the total number of “not good” days (mental and physical), with 30 days as the maximum assigned value. Healthy days are considered the positive complementary form of unhealthy days, all of which are calculated from responses to the Healthy Day measures.

The HRQoL-4 has been used extensively in the last several years in many U.S. nationwide studies and government programs, including those related to HIV/AIDS and cardiovascular health. Though developed and initially validated in the United States (Newschaffer, 1998), the HRQoL-4 instrument also has been validated in Canadian cities (Ôunpuu et al., 2000). Researchers administered the HRQoL-4 to 1,042 randomly selected adults in Hamilton, Ontario, and found that the patterns of association among HRQoL-4 questions, and the direction of the relationships among independent variables and HRQoL-4 were consistent with those hypothesized, thus validating the Healthy Days measures as a tool for monitoring health within a Canadian population. The HRQoL-4 has also been validated in specific Canadian demographic populations, such as the elderly, where physical and mental health and physical activity limitation were each shown to relate to self-perceived health (Ôunpuu et al., 2001).

The demonstrated ability of the HRQoL-4 in identifying health disparities, tracking population trends, and broadly measuring population health in Canada and abroad underlie its use in the health questionnaire. Given its extensive application in the US and in Canada, there will be a comprehensive dataset for comparative purposes.

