u) ... thyroid medication such as Synthroid or Levothyroxine?

- Yes
- No

v) ... any other medication?

- Yes - Specify
- No

Mental Health Information

MOOD (Bradburn Affect Balance Scale)

The next set of questions describes some of the ways people feel at different times. Please tell me if you have the feeling often, sometimes or never.

During the past few weeks, how often have you felt:

1. ... on top of the world?
Often
Sometimes
Never
DK, R (Finished Questionnaire)
2. ... very lonely or remote from other people?
Often
Sometimes
Never
3. ... particularly excited or interested in something?
Often
Sometimes
Never
4. ... depressed or very unhappy?
Often
Sometimes
Never
5. ... pleased about having accomplished something?
Often
Sometimes
Never
6. ... bored?
Often
Sometimes
Never
7. ... proud because someone complimented you on something you had done?
Often
Sometimes
Never

During the past few weeks, how often have you felt:

8. ... so restless you couldn't sit long in a chair?

- Often
- Sometimes
- Never

9. ... that things were going your way?

- Often
- Sometimes
- Never

10. ... upset because someone criticized you?

- Often
- Sometimes
- Never

11. Taking things all together, how would you say things are these days?

Would you say you're:

- 1 ... very happy?
- 2 ... pretty happy?
- 3 ... not too happy?

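### The Bradburn scale is one of two psychosocial outcome instruments, but the protocol summarizes its eleven items separately and so yields no scale-level measure for the planned comparisons

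*Protocol*

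**What the plan says.** The Synopsis lists four outcome measures. The second is "Current reported psychosocial health status as determined by the Bradburn Affect Balance Scale and the Health Related Quality of Life-4 scale". Two instruments therefore share this outcome.

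Section 3.2.1.3.1 introduces the first as "Eleven questions taken from the Bradburn Affect Balance Scale, a measurement of psychological well-being" and gives its structure: "Five questions reflecting positive feelings and five questions reflecting negative feelings", plus a final item on overall happiness. On external comparison it adds: "The CCHS also draws upon the Affect Balance Scale for questions relating to mood". It concludes that a large comparison dataset is available.

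Section 6.2.1.5 states how the instrument will be reported: "There are eleven questions in this assessment tool for which their categorical responses will be summarized independently".

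For the second instrument, Section 3.2.1.3.2 defines a summary. Unhealthy days are the physical and mental days added together, "with 30 days as the maximum assigned value".

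Section 6.4 mentions neither instrument by name.

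**The concern.** A scale with positive and negative items is described as one measurement of well-being and named as an outcome instrument, yet the stated analysis stops at the items. Section 2.0 wants health status compared between areas of the city and with places outside it, and Section 6.4 singles out Area 3 (Rodney Street) against the rest. With eleven separate three-level distributions, five of them running in the opposite direction to another five, the items may disagree. The protocol has no rule for what to conclude if they do.

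What is at stake is the clarity of one answer. Section 3.2.1.3 says these questions are there mainly to respond to community concerns. A result read off whichever of eleven items happens to differ would serve that purpose poorly. A single summary fixed in advance would leave no such choice.

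**Working it through.** No sample size, power or alpha figure is attached to this outcome, so there is no figure of the plan to reproduce. Section 6.1.1 sizes the study on asthma and nickel sensitivity. The check is mainly a comparison of passages.

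**1. Item count and direction.** In Appendix 10.1, Mental Health, items 1, 3, 5, 7 and 9 are positive (on top of the world, excited or interested, pleased, proud, things going one's way). Items 2, 4, 6, 8 and 10 are negative (lonely, depressed, bored, restless, upset). Item 11 is overall happiness. 5 + 5 + 1 = 11, which agrees with Sections 3.2.1.3.1 and 6.2.1.5. Items 1 to 10 share one response set: Often, Sometimes, Never.

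**2. The two instruments side by side.**

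| | Bradburn | HRQoL-4 |
|---|---|---|
| Named in the Synopsis outcome | Yes | Yes |
| Summary score defined | None | Unhealthy days, capped at 30 (3.2.1.3.2) |
| Stated reporting | Eleven items independently (6.2.1.5) | Four questions described (6.2.1.3) |

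**3. What item tables can and cannot give.** Write B = P − N, with P the sum of the five positive items and N the sum of the five negative items.

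- Mean: mean(B) = sum of positive item means − sum of negative item means. Once a coding is chosen, a reader could rebuild this from complete item tables, provided the same people answered all ten items.
- Spread: Var(B) = Var(P) + Var(N) − 2 Cov(P, N). Var(P) and Var(N) themselves contain the covariances among the items. Separate item tables carry none of these, so they give no standard error, confidence interval or test for B. They also cannot show how many respondents have more negative than positive affect.

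The protocol states no coding and does not propose this reconstruction, so even the mean is not a planned result.

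**4. Size of the score under one possible coding.** With Never 0, Sometimes 1, Often 2 (my proposal; the protocol gives no scoring), each subscale runs from 5 × 0 = 0 to 5 × 2 = 10. The balance runs from 0 − 10 = −10 to 10 − 0 = +10, which is 21 possible values.

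**5. Multiplicity, as an upper bound only.** If each of the eleven items were tested at 5% and the tests were independent, with no true difference, the chance of at least one false positive would be 1 − 0.95^11 = 1 − 0.569 = 0.431. One balance score tested once has a chance of 0.05. Items from one affect scale are probably positively correlated, which would bring the 43% down. The documents give no correlations, so the true value cannot be stated.

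**The case against.** The strongest reply is that item-level reporting is a deliberate descriptive choice. The primary objective is to characterize health. The borrowed questions come from the CCHS and can be compared with it item by item. When items are reported one at a time, their opposite directions do no harm. Most of this stands: the item tables are a legitimate result, and Section 6.2.1.5 speaks of summarizing, not testing. It does not answer the need for one reading of the instrument in the area comparison.

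A reader might infer that the named psychosocial outcome is not produced at all. The documents do not support that. The outcome rests on two instruments, the HRQoL-4 has a defined score, and no section promises an affect balance score by name.

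A reader might also take 43% as the plan's error rate. It is not. Section 6.4 describes chi-square tests across strata for categorical data in general, but no mock table assigns a p-value to a Bradburn item.

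The absence of either instrument from the mock tables adds little, because other collected variables also have no row and table shells are often completed in an analysis plan. The routing at item 1, "DK, R (Finished Questionnaire", is a separate matter. The protocol gives no rate of such answers, and changing a skip that may come from the CCHS could cost comparability.

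Finally, this could be called detail for an analysis plan not shown here. That fails, because the protocol is not silent: it states an item-by-item method, and a plan that scored the scale would have to go beyond it.

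**Conclusion.** The point holds in a limited form. The protocol names the Bradburn scale as an outcome instrument and describes its positive and negative halves, then commits to eleven independent item summaries. The Bradburn component therefore has no planned scale-level measure for comparing Rodney Street with the rest of the city or Port Colborne with the CCHS.

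The practical weight is modest. This is one of two instruments for one of four outcome measures. It is descriptive and has no bearing on the sample size. The 43% figure applies only if all eleven items are tested at 5% and are independent. The conclusion itself rests on the text and not on that figure.

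**What to change.** In Section 6.2.1.5:

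- Define positive affect (items 1, 3, 5, 7, 9), negative affect (items 2, 4, 6, 8, 10) and balance (positive minus negative) under a coding stated before the data are seen. Never 0, Sometimes 1, Often 2 is one option. It is my suggestion and should be checked against the instrument's own scoring.
- Make the balance score the single mental-health summary for Area 3 against the other areas, and for the CCHS comparison where CCHS data can be scored the same way.
- Keep the item frequencies and the happiness item as secondary descriptive results.

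If the sponsor prefers to stay at item level, the Synopsis and Sections 3.2.1.3.1 and 6.2.1.5 should say so and claim no scale-level comparison.

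The cost is a few lines, a few derived variables and one table. No new data are collected from participants. The main limitation is external: the protocol does not say in what form the CCHS data will be available. Without respondent-level records that comparison may have to remain item by item.

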6.2.2 Medical tests

In addition to the health questionnaire-related measures described above, current health status will also be assessed using a number of medical test-related outcome measures. These measures will be described for the general medical laboratory screen tests, metal tests, and non-specimen related tests and data points.

6.2.2.1 General medical laboratory screen tests

The general medical laboratory screen tests will include a number of measures that are based on the collection of blood and urine. Blood-based measures will include both haematology measures and biochemistry measures. Haematology outcome measures will provide concentrations, counts and volumes for blood-based parameters. Biochemistry outcome measures will include concentrations of total bilirubin, creatinine, blood urea nitrogen, cotinine, TSH and fT4. Urinalysis outcome measures will include presence of blood, leukocytes, protein, and glucose as well as nitrate concentrations and pH levels.

These measures will be expressed both in terms of mean values and within reference range frequency counts. Where the distribution of measured values are found to be non-normal, median values will be presented rather than means.

6.2.2.2 Metal tests

The metal tests will assess levels of CoCs in blood or urine. Specifically, the mean specimen levels of nickel, copper, cobalt, and fractionated and non-fractionated arsenic will be evaluated. Three metal confounders will also be measured: mercury, lead and cadmium. Again, these measures will be expressed both as mean (or median) values and within reference range frequency counts.

6.2.2.3 Non-specimen related tests and data points

This battery of medical tests and assessments will include cardiovascular, respiratory, dermatology and general measures. Cardiovascular measures will be obtained via ECG and blood pressure tests. ECG tests are designed to exclude abnormal results across a number of different parameters and will include: sinus rhythm, QRS axis, P waves, PR interval, QRS complex, QT interval, ST segment, T wave and U wave. Blood pressure will also be assessed and abnormal results will be summarized in terms of frequency counts. Respiratory measures will include a breath CO test and a lung function test. Breath CO concentrations will be expressed in terms of whether they are above or below a smoking abstinence threshold value (this will be further validated using a cotinine plasma test). Outcome measures from the lung function test will include FEV1, FVC, and PEF. Finally, general measures will include height and weight to determine body

mass index that will aid in interpreting test results. Both means and frequency values will be used to represent these data.

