3.3.4 Medications

In this study, subjects will report their medication use in the health questionnaire. Medications could be related to both an exposure and a clinical health assessment. In these cases, the effect of the exposure may be masked by the use of a medication and thus make the relationship between the exposure and clinical outcome difficult to discern. One example in this study could be the presence of abnormal results when testing thyroid hormone levels. An individual may have results that are within normal ranges but that individual is taking thyroid medication. Thus, this potential confounder will need to be controlled for in the analyses.

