Comparison of the Mean Levels of Selected Biological Measures, by Sampling Areas,
CHAP Comprehensive Health Questionnaire, Fall 2002

	Area 3	Areas 1, 2, 4, 5	Total for Port Colborne	p-value [†]
	Mean (s.d)*	Mean (s.d)	Mean (s.d)*	
Haemoglobin				
White Blood Cell Count				
Red Blood Cell Count				
Haematocrit				
Mean Cell Volume of Red Cells				
Mean Hemoglobin Concentration of Red Cells				
Platelet Count				
Red Cell Distribution Width				
Mean Platelet Volume				
Differential Leukocyte Count				
Bilirubin				
Creatinine				
Plasma Cotinine				
Plasma Screen for Concentration of TSH				
Blood Urea Nitrogen				

[†] p-value is based on an ANOVA for comparing the means between Area 3, and Areas 1, 2, 4, and 5; after adjusting for difference in the age and sex distribution of the two populations.

* s.d. = standard deviation

Table 8.
Comparison of the Non-Specimen Tests Among Participants, by Sampling Areas,
CHAP Comprehensive Health Questionnaire, Fall 2002

	Area 3	Areas 1, 2, 4, 5	Total for Port Colborne	p-value [†]
	Mean (s.d) [*]	Mean (s.d)	Mean (s.d.)	
Calculated BMI				
Electrocardiogram	---	---	---	---
Blood Pressure				
Carbon Monoxide Breath Test				
Forced Expiratory Volume in 1 second				
Forced Vital Capacity				
Peak Expiratory Flow Rate				
Dermatology Patch: Nickel Sulfate				
Dermatology Patch: Cobalt Dichloride				

[†] p-value is based on an ANOVA for comparing the means between Area 3, and Areas 1, 2, 4, and 5; after adjusting for difference in the age and sex distribution of the two populations.

^{*} s.d. = standard deviation

Table 9.
Comparison of the Selected Measures of Chemicals Among Participants, by Sampling Areas, CHAP Comprehensive Health Questionnaire, Fall 2002

	Area 3	Areas 1, 2, 4, 5	Total for Port Colborne	p-value [†]
Chemical	Mean (s.d) [*]	Mean (s.d)	Mean (s.d)	
Nickel (Urine)				
Copper (Urine)				
Cobalt (Urine)				
Arsenic (Urine)				
Mercury (Urine)				
Lead (Blood)				

[†] p-value is based on an ANOVA for comparing the means between Area 3, and Areas 1, 2, 4, and 5; after adjusting for difference in the age and sex distribution of the two populations.

^{*} s.d. = standard deviation

Table 10.
Comparison of the Proportion of Tests Outside Normal Range for Selected Biological Measures,
by Sampling Areas,
CHAP Comprehensive Health Questionnaire, Fall 2002

	Area 3	Areas 1, 2, 4, 5	Total for Port Colborne	p-value [†]
Proportion Outside Normal Range				
Haemoglobin (normal range)				

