White Blood Cell Count (normal range)				
Red Blood Cell Count (normal range)				
Haematocrit (normal range)				
Mean Cell Volume of Red Cells (normal range)				
Mean Hemoglobin Concentration of Red Cells (normal range)				
Platelet Count (normal range)				
Red Cell Distribution Width (normal range)				
Mean Platelet Volume (normal range)				
Differential Leukocyte Count (normal range)				
Bilirubin (normal range)				
Creatinine (normal range)				
Plasma Cotinine (normal range)				
Plasma Screen for Concentration of TSH (normal range)				
Blood Urea Nitrogen (normal range)				

[†] p-value is based on logistic regression analysis controlling for differences in the age and sex distribution of the two sampling areas

Table 11.
Comparison of the Proportion of Non-specimen Tests Outside Normal Range, by Sampling Areas, CHAP Comprehensive Health Questionnaire, Fall 2002

	Area 3	Areas 1, 2, 4, 5	Total for Port Colborne	p-value [†]
Proportion Outside Normal Range				
Calculated BMI (average range)				
Electrocardiogram [‡]				
Blood Pressure (normal range)				
Carbon Monoxide Breath Test (normal range)				
Forced Expiratory Volume in 1 second (normal range)				
Forced Vital Capacity (normal range)				
Peak Expiratory Flow Rate (normal range)				
Dermatology Patch: Nickel Sulfate (normal range)				
Dermatology Patch: Cobalt Dichloride (normal range)				

[†] p-value is based on logistic regression analysis controlling for differences in the age and sex distribution of the two sampling areas

[‡] proportion with abnormal electrocardiogram

Table 12.
Comparison of the Proportion of Chemical Measures Outside Normal Range, by Sampling Areas, CHAP Comprehensive Health Questionnaire, Fall 2002

	Area 3	Areas 1, 2, 4, 5	Total for Port Colborne	p-value [†]
	Proportion Outside Normal Range			
Nickel (Urine) (normal range)				
Copper (Urine) (normal range)				
Cobalt (Urine) (normal range)				
Arsenic (Urine) (normal range)				
Mercury (Urine) (normal range)				
Lead (Blood) (normal range)				

[†] p-value is based on logistic regression analysis controlling for differences in the age and sex distribution of the two sampling areas.

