- Rhinitis
- Nasal Polyps
- Nasal Septal Ulceration
- Other, Please specify

19. How old were you when this was first diagnosed?

_____ Age in years
(MIN: 0) (MAX: current age)

Skin:

20. Do you have a skin condition?

- Yes
- No (Go to Q23)
- Don't Know, Refused (Go to Q23)

21. What type of skin condition do you have:

INTERVIEWER: Mark all that apply.

- 1 Dermatitis/eczema
- 2 Pigmentation change (skin darkening or lightening; "change in skin color")
- 3 Hyperkeratosis (skin thickening)
- 4 Other, Please specify

22. How old were you when this was first diagnosed?

_____ Age in years
(MIN: 0) (MAX: current age)

Cardiovascular:

23. Do you have high blood pressure? 

- Yes
- No (Go to Q25)
- Don't Know, Refused (Go to Q25)

24. How old were you when this was first diagnosed? 

_____ Age in years
(MIN: 0) (MAX: current age)

Remember, we're interested in conditions diagnosed by a health professional.

25. Do you have migraine headaches? 

Yes

No (Go to Q27)

Don't Know, Refused (Go to Q27)

26. How old were you when this was first diagnosed? 

____ Age in years

(MIN: 0) (MAX: current age)

27. Do you have heart disease? 

Yes

No (Go to Q29)

Don't Know, Refused (Go to Q29)

28. How old were you when this was first diagnosed? 

____ Age in years

(MIN: 0) (MAX: current age)

29. Have you ever had a heart attack (damage to the heart muscle)? 

Yes

No (Go to Q30)

30. Do you currently have angina (chest pain, chest tightness)? 

Yes

No (Go to Q31)

31. Do you currently have congestive heart failure (inadequate heart beat, fluid build-up in the lungs or legs)? 

Yes

No (Go to Q32)

Thyroid:

32. Do you have a thyroid condition? 

Yes

No (Go to Q34)

DK, R (Go to Q34)

33. How old were you when this was first diagnosed? 

____ Age in years

(MIN: 0) (MAX: current age)

Gastro-intestinal/Liver:

34. Do you have stomach or intestinal ulcers? 

Yes

No (Go to Q36)

DK, R (Go to Q36)

35. How old were you when this was first diagnosed? 

____ Age in years

(MIN: 0) (MAX: current age)

36. Do you have Gastroenteritis?

Yes

No (Go to Q38)

DK, R (Go to Q38)

37. How old were you when this was first diagnosed?

____ Age in years

(MIN: 0) (MAX: current age)

38. Do you have Jaundice?

Yes

No (Go to Q40)

DK, R (Go to Q40)

39. How old were you when this was first diagnosed?

____ Age in years

(MIN: 0) (MAX: current age)

Neurological:

40. Do you have Peripheral Neuropathy (numbness or tingling in fingers or toes)?

Yes

No (Go to Q42)

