Don't Know/Refused (Go to Q42)

41. How old were you when this was first diagnosed?

____ Age in years

(MIN: 0) (MAX: current age)

42. Do you have Parkinson's Disease? 

Yes (Go to Q44)

No (Go to Q44)

Don't Know/Refused

43. How old were you when this was first diagnosed? 
____ Age in years
(MIN: 0) (MAX: current age)

Reproductive Health:

44. Were you ever diagnosed with a fertility problem?
Yes, specify
No
Don't Know/Refused

45. If female, have you ever had any of the following adverse pregnancy outcomes?
1 Spontaneous Abortion/Miscarriage
2 Still Birth
3 Ectopic Pregnancy

Other:

46. Do you suffer from multiple chemical sensitivities? 
Yes
No (Go to Q48)
Don't Know/Refused (Go to Q48)

47. How old were you when this was first diagnosed? 
____ Age in years
(MIN: 0) (MAX: current age)

48. Do you have any other long-term conditions that have been diagnosed by a health care professional? 
Yes
No (Go to Q50)
Don't Know/Refused (Go to Q50)

49. Please specify other long-term conditions. 

Drug Use:

We'd like to ask a few questions about your use of medications, both prescription and over-the-counter.

50. In the past month, did you take: 

a) ... pain relievers such as aspirin or Tylenol (including arthritis medicine and anti-inflammatories)?

Yes

No

R (Go to Mental Health Section)

b) ... tranquilizers such as Valium?

Yes

No

c) ... diet pills such Redux, Ponderal or Fastin?

Yes

No

d) ... anti-depressants such as Prozac, Paxil or Effexor?

Yes

No

e) ... codeine, Demerol or morphine?

Yes

No

f) ... allergy medicine such as Seldane or Chlor-Tripolon?

Yes

No

g) ... asthma medications such as inhalers or nebulizers?

Yes

No

h) ... cough or cold remedies?

Yes

No

i) ... penicillin or other antibiotics?

Yes

No

j) ... medicine for the heart?

Yes

No

k) ... medicine for blood pressure?

Yes

No

l) ... diuretics or water pills?

Yes

No

m) ... steroids?

Yes

No

n) ... insulin?

Yes

No

o) ... pills to control diabetes?

Yes

No

p) ... sleeping pills?

Yes

No

q) ... stomach remedies?

Yes

No

r) ... laxatives?

Yes

No

If female & age ≤ 49 ,

s) ... birth control pills?

Yes

No

If female & age ≥ 30 ,

t) ... hormones for menopause or aging symptoms?

Yes

No

DK, R

t.1) What type of hormones are you taking?

INTERVIEWER: Read categories to respondent.

- 1 Estrogen only
- 2 Progesterone only
- 3 Both
- 4 Neither

t.2) When did you start this hormone therapy?

|_|_|_| Year

(MIN: year of birth + 30) (MAX: current year)

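### Section 3.3.4 says medication masking must be controlled for, but Tables 8 and 11 compare measured blood pressure between areas with adjustment for age and sex only

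*Protocol*

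**What the plan says.** Section 6.2.2.3 defines the measured outcome: "Blood pressure will also be assessed and abnormal results will be summarized in terms of frequency counts". In section 6.5.1, Table 11 has a row "Blood Pressure (normal range") under the proportion outside normal range, comparing Area 3 with Areas 1, 2, 4 and 5. Its footnote reads: "p-value is based on logistic regression analysis controlling for differences in the age and sex distribution of the two sampling areas". Table 8 compares mean blood pressure between the same groups by ANOVA, "after adjusting for difference in the age and sex distribution of the two populations".

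Section 3.3.4 says that medication use can be related to both an exposure and a clinical assessment and can hide the effect of the exposure. Thyroid testing is its example: "An individual may have results that are within normal ranges but that individual is taking thyroid medication". It concludes: "Thus, this potential confounder will need to be controlled for in the analyses". Section 3.4 lists prescription medications among the confounders to be taken into account. Section 3.2.2.5 limits the thyroid validation to untreated people. No sentence says how people treated for high blood pressure enter Tables 8 and 11.

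The information needed is collected. In Appendix 10.1, item 50k of the drug-use questions asks about "medicine for blood pressure" in the past month and item 50l about diuretics, neither restricted to adults. Item 23 asks "Do you have high blood pressure", under an introduction that limits the section to conditions diagnosed by a health professional.

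**The concern.** An in-range reading has two different meanings here: the person does not have hypertension, or has it and treatment is holding it down. Table 11 puts both in the normal group. In Table 8 the treated reading enters the mean at its lowered value. If residents of the Rodney Street area are treated, or brought under control, less often or more often than other residents of the same age and sex, the measured comparison can show an area effect where disease is equal, or show none where disease differs. A reader would probably take such a result as evidence about exposure.

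Section 3.3.4 describes this mechanism and commits the analysis to dealing with it. The footnotes that fix the area comparisons do not.

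**Working it through.** The protocol gives no blood pressure rate, threshold or power, so there is no stated figure to reproduce. The check has two parts.

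**1. Setting the sections side by side.**
- Section 3.3.4: medication masking is to be controlled for (general statement, thyroid as the example).
- Table 8 and Table 11 footnotes: age and sex only.
- Section 3.3: unadjusted, age-and-sex, and fully adjusted models. The last could admit medication as a covariate, but that is a weak repair. Blood-pressure medicine is a consequence of the condition being measured, and adjusting for it does not move treated in-range people out of the normal group.

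**2. How large the distortion could be.** Inputs:
- H, true prevalence of hypertension, equal in both areas (assumed).
- c, share of cases held in range by treatment, c3 in Area 3 and cR elsewhere (assumed).
- 500 people per area, from section 6.1.1; two-sided 5% test.

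Formulas:
- Proportion measured abnormal: a = H × (1 − c3) in Area 3, b = H × (1 − cR) elsewhere.
- False odds ratio: [a/(1 − a)] / [b/(1 − b)].
- Chance of p<0.05 ≈ Φ(|a − b|/SE − 1.96), with SE = √[a(1 − a)/500 + b(1 − b)/500].

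Worked case, H = 20%, c3 = 30%, cR = 50%: a = 0.20 × 0.70 = 0.14 and b = 0.20 × 0.50 = 0.10. Odds ratio = (0.14/0.86)/(0.10/0.90) = 1.47. SE = 0.0205, so 0.04/0.0205 = 1.95, and the chance of p<0.05 is about 50%.

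The range, with H = 20% in both areas:

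| Control, Area 3 v elsewhere | Measured abnormal | False odds ratio | Chance of p<0.05 |
|---|---|---|---|
| 30% v 30% | 14% v 14% | 1.0 | 5% |
| 30% v 40% | 14% v 12% | 1.19 | about 16% |
| 20% v 40% | 16% v 12% | 1.40 | 45% |
| 30% v 50% | 14% v 10% | 1.47 | about 50% |
| 20% v 60% | 16% v 8% | 2.19 | 97% |

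Prevalence matters less than the gap in control. With 20% v 40%, the odds ratio is 1.38 at H = 15% and 1.44 at H = 30%.

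The bias can also run the other way. With true prevalence of 30% v 20% (odds ratio 1.71) and control of 60% v 40%, measured abnormal is 0.30 × 0.40 = 12% v 0.20 × 0.60 = 12%, and the difference disappears.

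Under the same model, counting a person as affected if measured out of range or on medicine gives a + H × c3 = H in Area 3 and b + H × cR = H elsewhere. The odds ratio is then 1.0 whenever true prevalence is equal.

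**The case against.** Several points on the other side are sound.

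- A reader might infer that the protocol recognises masking only for thyroid tests. It does not: section 3.3.4 is general, and section 3.4 repeats the point for prescription medications. The gap is that a stated commitment does not reach two tables.
- A reader might infer that treated hypertension is lost, or that city-wide prevalence is badly understated. The documents do not support this. Table 5 compares hypertension by area and Table 6 compares it with Ontario, using the diagnosed-condition question, which can include treated people. Table 11 reports readings and is not labelled as prevalence of hypertension. Still, self-reported diagnosis does not correct the measured comparison, and nothing says how to read Tables 5 and 11 if they disagree.
- Measured health status is itself a planned outcome, and an in-range reading is a correct measurement. This is a good reason to keep the measured-only row.
- The wording that treated people count as normal fits Table 11 only and follows from the protocol's silence. In Table 8 the effect is a lowered mean.
- Blood pressure is one row among many. It is not in the power calculation, and the ECG also addresses cardiovascular health.
- Detail of this kind is often left to a statistical analysis plan, and the mock tables are shells. That would carry more weight if the footnotes did not state the adjustment set.

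The scenarios are assumptions, and with equal control between areas there is no false difference.

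**Conclusion.** The point holds as an inconsistency with a cheap repair. As written, Tables 8 and 11 would carry a bias that section 3.3.4 says must be controlled for. Its direction and size are unknown. In the scenarios above, with equal true prevalence of 20%, the false odds ratio runs from 1.0 with equal control to about 2.2 with control of 20% v 60%; a 20-point gap gives 1.40 to 1.47.

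These figures assume that every uncontrolled case reads out of range and nobody else does, that control is achieved with medicine reported at item 50k, and that the gap in control remains after age and sex adjustment. The protocol supplies no evidence that such a gap exists. The finding is therefore that the planned comparison cannot separate treatment from disease. It does not show that a false area effect is to be expected.

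**What to change.** In Table 11, keep the measured-only row and add a row for measured out of range or current use of blood-pressure medicine (item 50k). Base any area comparison of hypertension on the new row.

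For Table 8, add a sensitivity analysis for readings of medicated people. Either treat each such reading as a lower bound for the untreated value (censored), or show means by medication use. Do not rely on entering medication only as a covariate. State in the footnotes of both tables that this implements section 3.3.4.

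The cost is one definition, one extra row and one sensitivity analysis, all from data already collected. The downside is that some people take these medicines for other reasons and would be counted as hypertensive, which is why the two rows should be shown together.
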